11.4.1 Datasets to be analyzed, analysis populations

The full analysis set (FAS) will include **all patients who gave written informed consent and were enrolled**. Patients in the FAS will be analyzed according to the randomly assigned treatment, adhering to the intention-to-treat principle.

The per protocol set (PPS) will include all patients from the FAS who are **Mp PCR-positive** (section 6.1, Table 5) and who are sufficiently compliant to treatment ($\geq 80\%$ of the medication used).

The strict per protocol set (strict PPS) will include all patients from the PPS who additionally have **confirmed Mp infection by IgM ASC ELISpot assay** (section 6.1, Table 5).

Patients in the PPS and strict PPS will be analyzed according to the received treatment (in case there are any deviations from the randomized treatment).

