11.4.2 Primary analysis

To assess the non-inferiority of placebo vs. azithromycin regarding the co-primary endpoint **time to**

normalization of VS, we will estimate the hazard ratio of placebo vs. azithromycin with a two-sided 97.5% CI using a Cox proportional hazards model on the PPS (defined in section 11.4.1). Non-inferiority of placebo will be declared if the lower limit of the CI will be larger than the non-inferiority margin (i.e., the whole CI lies entirely above the margin).

To assess the non-inferiority of placebo vs. macrolide regarding the co-primary endpoint **CAP-related change in patient care status**, we will estimate the absolute risk difference ($ARD = risk_{azithromycin} - risk_{placebo}$) with a two-sided 97.5% CI on the PPS. Non-inferiority of placebo will be declared if the lower limit of the CI will be larger than the non-inferiority margin (i.e., the whole CI lies entirely above the margin).

The two non-inferiority tests will be performed and interpreted independently (of each other) and the trial considered successful if non-inferiority can be shown for at least one of the primary outcomes. Should the resulting CIs exclude the reference value for no difference (1 for hazard ratio, 0 for ARD), the result can be interpreted as superiority of either treatment [88].

To complement the main analyses above, the following sensitivity and additional analyses are planned:

- We consider the **PPS as the main set for showing non-inferiority** (section 6.1, Table 5), and the sample size calculation was also done with regard to the PPS (section 11.2). In addition, we will also test non-inferiority in the strict PPS and the FAS. Since the three analysis sets (FAS, PPS, and strict PPS) differ considerably in size and composition (section 6.1, Table 5), we will consider the PPS as the relevant set for concluding non-inferiority, but we will discuss differences in the conclusions based on the different sets. For a robust interpretation of the non-inferiority test these analyses should lead to similar conclusions as the main analysis [87].
- For CAP-related change in patient care status, we will present the 2×2 table of events per treatment arm and an unadjusted odds ratio (OR) estimate for all three analysis sets.
- For time to VS normalization, we will plot Kaplan-Meier curves and estimate median time-to-event by trial arm.

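### Superiority of either treatment may be read from per-protocol confidence intervals, which rest on a compliance-filtered, as-received comparison and not on the groups as randomized

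*Protocol*

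**What the plan says.** Protocol section 11.4.2 defines two confidence intervals. For time to normalization of vital signs (endpoint 1.1), the hazard ratio is estimated "with a two-sided 97.5% CI using a Cox proportional hazards model on the PPS". For change in patient care status (endpoint 1.2), the absolute risk difference is estimated "with a two-sided 97.5% CI on the PPS". After the non-inferiority rules, the section says that if these intervals exclude 1 or 0 respectively, "the result can be interpreted as superiority of either treatment". No other intervals have been defined at that point, so the sentence refers to the PPS intervals.

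Section 11.4.1 builds the PPS from PCR-positive children "who are sufficiently compliant to treatment", meaning at least 80% of the medication used, and adds: "Patients in the PPS and strict PPS will be analyzed according to the received treatment". For the full analysis set (FAS) it says: "Patients in the FAS will be analyzed according to the randomly assigned treatment, adhering to the intention-to-treat principle".

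The FAS enters section 11.4.2 only among the sensitivity and additional analyses: "In addition, we will also test non-inferiority in the strict PPS and the FAS". The choice of deciding set is also worded for that purpose: "we will consider the PPS as the relevant set for concluding non-inferiority". Nothing in the protocol moves the superiority reading to an as-randomized set, or requires the FAS to agree before superiority is claimed.

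**The concern.** A per-protocol set can be defended as the main set for non-inferiority. A superiority claim asks whether one arm is truly better, and it rests on the arms being comparable by randomization. The PPS weakens that in two ways: membership depends on how much medication was taken after randomization, and arm membership follows the treatment received.

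The protocol itself links medication use to outcome. Table 6 (section 6.3) names ICU transfer as an example of a reason to stop the study medication, and section 5.1 counts ICU transfer as an endpoint 1.2 event. An event can therefore remove its own patient from the set in which events are counted. If such losses were more frequent in one arm, that arm would look better than it is. A headline that placebo is superior to azithromycin could then arise without any true effect.

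**Working it through.** **1. The plan's own figures.** Inputs from section 11.2: one-sided alpha 1.25% (z = 2.241), power 80% (z = 0.842), HR margin 0.7, event rate 99%, risk 5% in both arms, ARD margin 7.5 points, drop-out 14.5%.
- Endpoint 1.1: events = 4 × (2.241 + 0.842)² / (ln 0.7)² ≈ 299; 299 / 0.99 ≈ 302 children; 302 / 0.855 ≈ 354 enrolled. This matches the protocol.
- Endpoint 1.2: n per arm = (2.241 + 0.842)² × 2 × 0.05 × 0.95 / 0.075² = 160.5, so 161 per arm and 322 in all; 322 / 0.855 = 376.6, stated as 376. This agrees apart from rounding.

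**2. Alpha.** A two-sided 97.5% interval spends 2.5% two-sided per endpoint, hence at most 5% over both, and 1.25% in the direction of placebo. The level is sound; the analysis set is the issue.

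**3. When a child leaves the PPS.** From the volumes in Table 7:
- 10 to <15 kg: three doses are 2.50 + 2 × 1.25 = 5.00 of 7.50 mL = 66.7%; four doses are 6.25 / 7.50 = 83.3%.
- 15 to <20 kg: three doses are 3.75 + 2 × 2.00 = 7.75 of 11.75 mL = 66.0%; four doses are 9.75 / 11.75 = 83.0%.
- The other bands give the same shares as the first.

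A child stopped after dose 3 or earlier falls below 80%; a child who takes four doses stays in.

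**4. Which filter matters.** PCR status comes from a swab taken on day 1, before treatment can affect it. PCR-positive children analysed as randomized therefore remain a randomized comparison. The compliance filter and the as-received assignment do not have this property.

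**5. Size for endpoint 1.1 with no true effect.** Exponential times with 99% normalized by day 28: rate = ln(100) / 28 = 0.1645 per day, median 4.2 days as in section 11.2, and 44% not normalized by day 5. There are 161 children per arm after exclusion. *Assumption, not a protocol figure:* a share s of the placebo arm, drawn from those not normalized by day 5, is excluded, and none of the azithromycin arm. Simulations of 6,000 to 10,000 trials gave:

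| s | Mean HR | Lower 97.5% limit above 1 |
|---|---|---|
| 0% | 1.00 | 1.2–1.4% (nominal 1.25%) |
| 5% | 1.04 | 3.1–3.3% |
| 8% | 1.08 | 6.2–6.7% |

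Drawing the excluded children from the slower half of the arm instead gives 2.9% and 4.3% for s = 5% and 8%. Excluding the same share of slow recoverers from both arms gives 1.4% and 1.8%, near nominal.

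For scale: section 11.2 allows 5% for loss to follow-up or insufficient compliance. Of 376 × 0.90 = 338 PCR-positive children that is about 17, or 10% of one arm of 169 if all fell there.

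**6. Endpoint 1.2, same caution.** True risk is 5% in both arms, with 161 per arm and Wald intervals (an assumption). If a share f of placebo events is excluded, the observed placebo risk is 0.05(1 − f) / (1 − 0.05f): 3.8% for f = 25% and 2.6% for f = 50%. False placebo superiority is then 4.0% and 12.5%, against 1.2% with none excluded.

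**7. Cost in precision of changing the set.** The smallest HR departures that exclude 1 are exp(±2.241 × √(4 / (0.99N))):
- PPS (N = 322): 0.778 or 1.285
- PCR-positive as randomized (N = 338): 0.783 or 1.278
- FAS (N = 376): 0.793 or 1.262

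Neither alternative loses precision.

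**The case against.** Superiority is neither an objective (section 4.2) nor a hypothesis (section 11.1). Trial success rests on non-inferiority, and the sentence only permits the reading. FAS analyses are planned for both endpoints, and differences between sets are to be discussed. The trial is double-blind, expected non-compliance is low, and as-received assignment matters only if a child received the wrong treatment. Deterioration does not automatically end study medication: Table 6 treats admission and severe distress as grounds for modification, and its footnote asks for the five days to be completed whenever possible. A child also has to stop by dose 3 to leave the set, so many slow recoverers cannot be lost this way.

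Most of this stands, and it limits the size. It does not remove the point. The commitments about other sets are worded for non-inferiority, and blinding does not prevent differential deterioration or side effects from driving exclusions.

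A reader might infer more than the documents support:
- *That children who deteriorate generally leave the PPS.* Some may; the protocol often keeps them on study medication.
- *That gastrointestinal events under azithromycin would bias the result the other way.* That needs a link between those events and recovery, which the protocol does not give. Section 3.6 cites mild symptoms in 1.3% of azithromycin-treated children in one trial, with no discontinuation.
- *That only the FAS could carry a superiority claim.* PCR-positive children analysed as randomized would serve as well.
- *That the non-inferiority decision is affected.* The choice of the PPS there is a separate matter.

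**Conclusion.** The point holds as a weakness in the stated rule, and the sentence should be changed. As written, superiority of either arm may be claimed from a set filtered by post-randomization compliance and analysed as received, with no requirement that an as-randomized analysis agree. The documents do not fix the size of any bias. Under the one-arm worst case of step 5, false placebo superiority on endpoint 1.1 rises from 1.25% to about 3% with 5% exclusion and to 6 to 7% with 8%. These rates rest on the assumed exclusion shares and selection rule. Milder selection gives less, and non-differential exclusion gives almost nothing.

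**What to change.** Replace the superiority sentence in section 11.4.2 with: *Superiority will be concluded only if the two-sided 97.5% CI in the FAS, analysed as randomized, excludes the null value; the PPS result is supportive.*

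If the sponsor prefers to keep the *Mp* target population, prespecify instead all PCR-positive patients, analysed as randomized regardless of compliance, as the set for superiority. Either choice should be fixed before unblinding.

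The cost is one sentence. The FAS analysis is already planned, and the PCR-positive version needs no further data. No patients are added, and alpha, the non-inferiority rule and the sample size stay as they are. The downside of the FAS is slight dilution by about 10% PCR-negative children (section 11.2), which the second option avoids.

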Statistical considerations:	
Multiplicity with two co-primary endpoints was handled using the “at least one” success criterion: We estimated the sample size for both co-primary endpoints for a one-sided significance level of 1.25% and a power of 80%, and use the larger of the two sample sizes for the trial. This assures a minimum power of 80% to reject at least one null hypothesis.
 
The co-primary endpoint time to normalization of all VS is considered as a time-to-event endpoint. The sample size was estimated assuming an overall event rate of 99% and a hazard ratio of 1 for placebo vs. macrolide (a hazard ratio <1 would indicate longer duration with placebo than with macrolide). The sample size was estimated to show the non-inferiority of placebo vs. macrolide in Mp PCR-positive patients using a non-inferiority margin of 0.7 for the hazard ratio. Considering a drop-out rate of 14.5%, 354 patients should be recruited for the intervention phase of this study (302 evaluable patients).
 
For the co-primary endpoint CAP-related change in patient care status (binary) we expect an absolute risk of 5% in both trial arms and thus an absolute risk difference (ARD, $risk_{macrolide} - risk_{placebo}$) of 0 between the two arms. An ARD <0 would indicate a higher risk with placebo than macrolide. The sample size was estimated to show the non-inferiority of placebo vs. macrolide in Mp PCR-positive patients, using a non-inferiority margin of -7.5% for the ARD. Considering a drop-out rate of 14.5%, 376 patients should be recruited for the intervention phase of this study (322 evaluable patients).

GCP statement:	
This study will be conducted in compliance with the protocol, the current version of the Declaration of Helsinki, ICH-GCP, as well as all national legal and regulatory requirements.

ABBREVIATIONS

AE	Adverse event
AESI	Adverse event of special interest
AMR	Antimicrobial resistance
AR	Adverse reaction
ARD	Absolute risk difference
ASC	Antibody-secreting cell
ASR	Annual safety report
BASEC	Business Administration System for Ethical Committees (https://submissions.swissethics.ch/en/)
BTS	British Thoracic Society
CA	Competent authority (e.g., Swissmedic)
CAP	Community-acquired pneumonia
CEC	Competent ethics committee
CI	Confidence interval
ClinO	Ordinance on Clinical Trials in Human Research (in German: KlinV, in French: OClin, in Italian: OSRUm)
CTCAE	Common terminology criteria for adverse events

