Rationale: The resolution of all VS abnormalities has been proposed as an important primary endpoint for antibiotic trials in childhood pneumonia by the IDSA [62]. In contrast to adults, severe morbidity and mortality from CAP is minimal in children, particularly for *Mp* CAP (section 3.5 and 3.7). Previous trials on macrolides for *Mp* CAP have mainly focused on fever duration as a key endpoint [31, 32]. In the myCAP study, the median body temperature (T) at presentation among myCAP patients was 39.1°C (IQR, 39.0-39.7), and the clinical diagnosis of CAP based on fever and tachypnea could be radiologically confirmed in 98% of the cases [43]. On room air, 17% *Mp* CAP patients had an SpO₂<93% and required additional oxygen supply. The median fever duration for *Mp* CAP children was 2 days. There were no statistically significant differences between patients with or without antibiotic treatment for *Mp* [43]. Lu et al. [63] observed a mean fever duration of 5 days (no statistically significant differences between patients treated with macrolides or placebo). To conclude, this study will use VS measurements taken at the timepoint before randomization as baseline measurements. The VS measurements will be followed up until normalization of VS to reference values. We expect a rate of <1% of patients' VS not normalizing within a 28-day FUP. In agreement with the IDSA considerations [62], an assessment of the time to VS normalization (T, RR, HR, SpO₂) has been selected to be of main interest for MYTHIC.

1.2: CAP-related change in patient care status within 28 days (safety)

Defined as any change in patient care status from an ambulatory to hospitalized setting (admission or re-admission), or from a hospitalized on general ward to an ICU setting (ICU transfer).

Specific measurement: Incidence of (re-)admission to hospital or transfer to the ICU.

Analysis metric: Final value.

Method of aggregation: Proportion.

Time point: Within 28 days after randomization.

Rationale: We expect the placebo to be non-inferior to macrolides treatment regarding a CAP-related change in patient care status. This non-inferiority will be assessed by the incidence of (re-)admission to

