The primary endpoint **time to normalization of all VS** is considered as a time-to-event endpoint, i.e., the number of days until normalization. Although we expect all patients to normalize VS during the 28-day FUP period, we used an overall event rate of 99% for the sample size calculation, in order to allow censoring. This endpoint will be compared between trial arms by a Cox proportional hazards model to estimate a hazard ratio for placebo vs. azithromycin (a hazard ratio <1 would indicate longer duration to normalization with placebo than with azithromycin). We expect no difference between treatments and thus a hazard ratio of 1. The sample size was estimated to show the non-inferiority of placebo vs. azithromycin treatment in *Mp* PCR-positive patients using the method given in Chow et al. [84] (page 177), with a non-inferiority margin (δ_{HR}) of 0.7 for the HR. Assuming exponential survival times (with an overall event rate of 99% within 28 days), this non-inferiority margin of 0.7 would be equivalent to the inverse ratio of median survival times, which would be 4.8 days for placebo and 3.3 days for azithromycin (with a HR of 1 the median survival time would be 4.2 days). The maximum prolongation of the duration to VS normalization by 1.5 days may be acceptable from a clinical perspective, especially when weighed against side effects, effect of antibiotics on microbiome, increased antibiotic resistance, and costs. These aspects are also discussed for patients with group A β -hemolytic streptococcal pharyngitis, in which modest effects of antibiotics have been observed (symptomatic improvement by only 1-2 days) [85]. Under the assumptions stated above, 302 *Mp* PCR-positive patients are needed for this study (Figure 2). Considering a drop-out rate of 14.5%, 354 patients should be enrolled. This drop-out rate is calculated from an expected drop-out of 10% due to negative *Mp* PCR (false-positive screening by *Mp* IgM LFA, section 6.1, Table 5) and an additional overall drop-out rate of 5% (due to loss to FUP or insufficient compliance), i.e., $0.1 + 0.05 \cdot (1 - 0.1) = 0.145$ (14.5%).

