- Covariate-adjusted analyses will be performed for both endpoints and all analysis sets, considering all variables used in the minimization for treatment allocation (section 6.2.1). For time to VS normalization, a mixed-effects Cox proportional hazards model with a random intercept per center will be used [88]. For change in patient care status, a generalized linear mixed-effects model will be used. Explanatory variables in both models are treatment (placebo vs. azithromycin), age (continuous), patient care status (ambulatory vs. hospitalized), and prodromal symptom duration (continuous).

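### The adjusted Cox model for time to vital-sign normalization omits the index vital signs, so it cannot show whether the hazard ratio holds up against imbalance in baseline severity

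*Protocol*

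**What the plan says.** Co-primary endpoint 1.1 (section 5.1) is the time until temperature, respiratory rate, heart rate and SpO2 are all normal on three consecutive readings within 24 hours. The starting values are measured before randomization or before any antipyretic in the emergency department (sections 5.1, 9.2.1 and 9.3.4). The rationale in section 5.1 is explicit about their role: "this study will use VS measurements taken at the timepoint before randomization as baseline measurements".

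The deciding efficacy analysis in section 11.4.2 estimates the hazard ratio "using a Cox proportional hazards model on the PPS" and names no covariate. The same section adds complementary covariate-adjusted analyses in all analysis sets and fixes their content: "Explanatory variables in both models are treatment (placebo vs. azithromycin), age (continuous), patient care status (ambulatory vs. hospitalized), and prodromal symptom duration (continuous"). The Cox version also has a random intercept per center. These are the minimization variables of section 6.2.1. The subgroup models in section 11.4.3 use age, care status, prodromal duration, laboratory confirmation, chest radiograph and sex.

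The index vital signs are not minimization factors and appear in none of these models.

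**The concern.** When the endpoint is the time for four measurements to return to normal, how abnormal they were at the start is the obvious prognostic factor. Section 5.1 reports that 17% of the earlier *Mp* CAP cohort had SpO2 below 93% and needed oxygen. Fever may qualify on parent report from the last 24 hours (section 7.1), so some children can be below 38.0°C at index while others are well above it.

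The purpose of a prespecified adjusted analysis is to show that the treatment estimate does not rest on unequal prognosis between arms. An adjusted model without the endpoint's own baseline cannot do that for the factor most likely to matter. The protocol itself closes the covariate list, so this is not a detail it leaves to the statistical analysis plan. Choosing these covariates after the data are seen would be open to challenge, because section 6.2.2 has the statistician unblinded for the final analysis.

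**Working it through.** **1. The plan's own figures.** Inputs from the synopsis and section 11.2: one-sided alpha 1.25%, power 80%, margin 0.7, true hazard ratio 1, event rate 99%, drop-out 14.5%.

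- Events = 4 × (2.2414 + 0.8416)² / (ln 0.7)² = 4 × 9.505 / 0.1272 = 298.9.
- Patients = 298.9 / 0.99 = 301.9, so 302. Enrolled = 302 / 0.855 = 353.2, so 354. Both match.
- Exponential rate = −ln(0.01) / 28 = 0.1645 per day. Median = 0.693 / 0.1645 = 4.2 days, as stated ("with a HR of 1 the median survival time would be 4.2 days").
- The care-status endpoint sets the trial size at 322 evaluable patients, 161 per arm. Expected vital-sign events: 322 × 0.99 = 319.

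The formula contains no covariate, and section 11.2 justifies the margin by a ratio of the two arms' medians (4.8 and 3.3 days). The 0.7 margin is therefore on the unadjusted, marginal scale.

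**2. Where baseline severity enters.**

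| Step | Variables | Index vital signs? |
|---|---|---|
| Minimization (6.2.1) | age, care status, symptom duration, center | no |
| Deciding Cox model (11.4.2) | treatment | no |
| Adjusted Cox model (11.4.2) | treatment, age, care status, prodromal duration, center | no |
| Subgroup models (11.4.3) | six listed variables | no |

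**3. Effect of a chance imbalance.** The prognostic strength of index severity is not in the documents, so I assume 1.25-, 1.5- or 2-fold change in hazard per SD of a severity score. The standard error of the difference in mean severity between arms is √(2/161) = 0.111 SD. The shift in log hazard ratio for an imbalance of that size is about 0.111 × ln(fold). The distance from 1 to the margin is |ln 0.7| = 0.357.

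| Fold per SD | Shift in log HR | Share of distance to margin |
|---|---|---|
| 1.25 | 0.111 × 0.223 = 0.025 | 7% |
| 1.5 | 0.111 × 0.405 = 0.045 | 13% |
| 2 | 0.111 × 0.693 = 0.077 | 22% |

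**4. Marginal against conditional hazard ratio.** Simulation of 2,000 trials per case: 161 per arm, median 4.2 days, censoring at day 28, one standard-normal severity score, two-sided 97.5% interval.

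| Fold per SD | Unadjusted HR when the within-severity HR is 0.70 | Non-inferiority declared when the unadjusted HR itself is 0.70 (nominal 1.25%) | Not normalized by day 28 at HR 1 |
|---|---|---|---|
| 1.25 | 0.71 | 0.7% | 1.4% |
| 1.5 | 0.73 | 1.1% | 2.5% |
| 2 | 0.76 | 1.4% | 5.3% |

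The simulation standard error at 1.25% is √(0.0125 × 0.9875 / 2000) = 0.25 percentage points, so the third column shows no inflation. At a true hazard ratio of 1, power is about 80% with or without the severity score.

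**5. Selection into the deciding set.** Section 11.4.1 restricts the per protocol set to children who used at least 80% of the medication and analyzes them by treatment received. Use of medication is determined after randomization. Table 6 in section 6.3 lists clinical change, such as need for ICU transfer, among the reasons for stopping study medication. Membership can therefore depend on severity, and imbalance in this set need not be chance alone.

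**The case against.** The strongest case against the point is that the primary analysis is sound without these covariates. A reader might infer that leaving out baseline severity dilutes the hazard ratio towards 1 and so inflates false claims of non-inferiority. Judged against a within-severity hazard ratio of 0.70, the unadjusted model does declare non-inferiority too often: about 1.5%, 3.2% and 6.8% in the three cases. But that judges the test against a different quantity from the one the protocol defines. The margin, the sample size and the deciding model are all marginal, and on that scale the error rate is nominal (step 4). The gap between the two hazard ratios is non-collapsibility, not bias, and it vanishes at the planned hazard ratio of 1. The 2-fold case also leaves 5.3% unresolved at day 28, whereas section 5.1 expects under 1%. This objection stands in full.

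Three further objections stand in part.

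- Chance imbalance is already allowed for in the unadjusted interval. That is true on average over trials, but it does not show whether one realized result depends on such an imbalance.
- Care status captures some severity, since children needing oxygen are likely to be inpatients, and required tachypnea narrows the spread of respiratory rate. Care status is still a two-level proxy and leaves temperature, heart rate and most of the SpO2 range unaccounted for.
- Adjusting for the minimization variables is a coherent rule, and baseline characteristics will be tabulated by arm. A table shows an imbalance but not what it does to the hazard ratio.

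**Conclusion.** The point holds as a gap in the adjusted analysis, not as a fault in the primary test. The protocol fixes an adjusted Cox model for endpoint 1.1 that leaves out that endpoint's own baseline, so the model cannot show whether a non-inferiority result is robust to baseline severity. This matters most in the per protocol set, which decides the claim and is partly selected after randomization.

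Under the assumed 1.25- to 2-fold effect per SD, a one-standard-error chance imbalance is worth 7% to 22% of the distance to the margin. A conditional hazard ratio of 0.70 would appear as about 0.71 to 0.76 unadjusted. Both ranges rest on an assumed prognostic strength, and the upper end fits poorly with the protocol's expected normalization rate. The documents support no claim of type I error inflation, loss of power or a wrong sample size: 302 and 354 reproduce. The change is worth making because it closes a real gap at the cost of wording.

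**What to change.** In section 11.4.2, add index vital-sign terms to the adjusted Cox model for endpoint 1.1, prespecified and chosen not to overlap. One option is continuous index temperature plus index SpO2 below 93% (yes/no). Another is the number of abnormal vital signs at index plus continuous index temperature, with temperature left out of the count to avoid entering it twice.

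Keep the unadjusted Cox model on the per protocol set as the deciding analysis. State that the adjusted hazard ratio is conditional on baseline severity, that the 0.7 margin was justified on the marginal scale, and that the two estimates may differ for that reason alone. Leave the adjusted care-status model unchanged: at 5% risk in 322 patients it has only about 0.05 × 322 = 16 events.

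The cost is protocol and analysis-plan wording, 2 to 3 degrees of freedom against about 300 to 319 events, and a conditional hazard ratio to explain beside the marginal one. No new data are needed. The added terms address selection into the per protocol set only so far as it acts through measured index severity.
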